7.7.2. Concomitant Procedures

A concomitant procedure is any therapeutic intervention (e.g., surgery/biopsy, physical therapy) or diagnostic assessment (e.g., blood gas measurement, bacterial cultures) performed between the time of the participant's Baseline Visit and last study visit.

7.8. Continuation of Treatment

No further provisions are made for access to the study treatment.

CONFIDENTIAL

The information contained herein may not be used, disclosed, or published without the written consent of
Biogen MA Inc.

8. DISCONTINUATION OF STUDY TREATMENT AND WITHDRAWAL OF PARTICIPANTS FROM THE STUDY

8.1. Discontinuation of Study Treatment

A participant must permanently discontinue study treatment for any of the following reasons:

- The participant becomes pregnant. Study treatment must be discontinued immediately (Note: Instructions for reporting the pregnancy are provided in Section 11.4.1).
- The participant withdraws consent to continue study treatment.
- The participant experiences an AE that requires permanent discontinuation of study treatment.
- The participant is unwilling or unable to comply with the protocol.
- At the discretion of the Investigator for medical reasons.
- At the discretion of the Sponsor or upon request of a regulatory authority.
- Lymphocyte count $< 0.5 \times 10^3/\mu\text{L}$ persisting for > 6 months. An initial lymphocyte count $< 0.5 \times 10^3/\mu\text{L}$ should be confirmed by repeat testing. If the value remains $< 0.5 \times 10^3/\mu\text{L}$ for > 6 months, the participant must permanently discontinue study treatment. Participants who permanently discontinue the study with a last measured lymphocyte count $< \text{LLN}$ will require additional follow-up to monitor their lymphocyte counts; see [Table 2](#).

The reason for discontinuation of study treatment must be recorded in the CRF.

In addition to the reasons provided above for permanent discontinuation of study treatment, study treatment must be temporarily withheld if any of the following laboratory parameters meet the following threshold limits:

- AST or ALT $> 3 \times \text{ULN}$; confirmed by repeat testing. If the value remains $> 3 \times \text{ULN}$ for ≥ 4 weeks after interruption of study treatment, the participant must permanently discontinue study treatment.
- eGFR $< 60 \text{ mL/min}/1.73 \text{ m}^2$; confirmed by repeat testing as soon as possible. If the eGFR remains $< 60 \text{ mL/min}/1.73 \text{ m}^2$ for ≥ 4 weeks after interruption of study treatment, the participant must permanently discontinue study treatment.
- Urine albumin to urine creatinine ratio $> 22.6 \text{ mg}/\text{mmol}$; confirmed by repeat testing as soon as possible. If the urine albumin to urine creatinine ratio remains $> 22.6 \text{ mg}/\text{mmol}$ for ≥ 4 weeks after interruption of study treatment, the participant must permanently discontinue study treatment.

CONFIDENTIAL

The information contained herein may not be used, disclosed, or published without the written consent of Biogen MA Inc.

Resuming study treatment after it has been temporarily withheld is to be considered on a case-by-case basis and must be discussed with the Medical Monitor.

8.2. Lost to Follow-Up

Participants will be considered lost to follow-up if they repeatedly fail to return for scheduled visits and are unable to be contacted by the study site.

The following actions must be taken if a participant fails to return to the study site for a required study visit:

- The site must attempt to contact the participant and reschedule the missed visit as soon as possible, counsel the participant on the importance of maintaining the assigned visit schedule, and ascertain whether the participant wishes to and/or should continue in the study.
- In cases in which the participant is deemed lost to follow-up, the investigator or designee must make every effort to regain contact with the participant. These contact attempts should be documented in the participant's medical record.
- Should the participant continue to be unreachable, that participant will be considered to have withdrawn from the study with a primary reason of lost to follow-up.

8.3. Withdrawal of Participants from the Study

Participants must be withdrawn from the study for any one of the following reasons:

- The participant withdraws consent for participation in the study.
- The participant enrolls into another interventional clinical study in which an investigational treatment or approved therapy for investigational use is administered.
- The participant is unwilling or unable to comply with the protocol.

The primary reason for the participant's withdrawal from the study must be recorded in the participant's CRF. Any participant who prematurely discontinues study treatment or withdraws from the study will be asked to return to the clinic to complete all study assessments for Visit 14/ET Visit as well as the Safety Follow-Up Visit 2 weeks later (Visit 15).

Participants should undergo an ET visit unless withdrawal is due to death or withdrawal of consent. Participants who withdraw from the study for reasons other than safety may be replaced at the discretion of the Sponsor.

Participants with intense PK sampling who withdraw early or require dose reduction or samples not collected per protocol or laboratory manual, may be replaced at the discretion of the Sponsor.

CONFIDENTIAL

The information contained herein may not be used, disclosed, or published without the written consent of
Biogen MA Inc.

9. [REDACTED], PHARMACOKINETIC, AND PHARMACODYNAMIC ASSESSMENTS

See Section 1.3 for the timing of all assessments.

Tests and evaluations affecting primary endpoints and/or analyses may need to be repeated if the original results are lost or damaged. In these cases, participants will be asked to return to the study site to have the evaluations repeated.

9.3. Pharmacokinetic Assessments

The subset of 7 Japanese participants must be in the overnight fasted state (10 hours) prior to administration of the dose of DRF on study Day 29, and no food will be allowed for at least 4 hours after the dose of DRF. Participants will be allowed water ad libitum, except for 1 hour before and 2 hours after administration of the dose of DRF.

For the subset of 7 Japanese participants with intensive blood sample collection for PK analysis of metabolites MMF and HES, samples will be obtained at the following:

- -30 to 0 minutes (predose) and at 0.5, 1, 2, 3, 4, 6, and 8 hours (postdose)
- For intensive PK sampling for MMF and HES, noncompartmental plasma PK parameters (AUC_{last} , C_{max} , t_{max} , and $t_{1/2}$ [MMF only]) will be calculated. The PK parameters (AUC_{last} , C_{max} , t_{max}) for MMF and HES in Study 272MS303 will be compared with those in Study ALK8700-A301.

CONFIDENTIAL

The information contained herein may not be used, disclosed, or published without the written consent of Biogen MA Inc.

In addition, sparse blood samples will be collected for PK analysis of the metabolites MMF and HES as follows:

- On Day 29, blood samples will be collected -30 to 0 minutes (predose) and 2 to 3 hours (postdose) for participants with sparse blood sample collection (approximately 43 per Japanese cohort and 50 per Chinese cohort).
- On Day 57, blood samples will be collected -30 to 0 minutes (predose) and 2 to 3 hours (postdose) for all participants with sparse blood sample collection (approximately 50 per cohort).
- Participation in the sparse PK cohort does not preclude enrollment in the intensive PK cohort as well. In the event that a participant is enrolled in both the sparse and intensive PK cohorts and intensive PK sampling was completed on Day 29 or Day 57 for a participant, sparse PK sampling will not be required for said days. However, if it is determined that intensive PK is not feasible by Day 57, sparse PK sampling will be completed according to protocol and intensive PK should be completed at later visits.

The PK sample volume will be approximately 6 mL for each individual sample. For the intensive PK sampling group, there are a maximum of 10 PK sample collection timepoints planned (8 timepoints on Day 29 for the intensive PK sampling and 2 timepoints on Day 57 for the sparse PK sampling). In the advent that intensive PK sampling is not feasible by Day 57, there are a maximum of 12 PK sample collection timepoints planned (2 timepoints on Day 29 and on Day 57 for the sparse PK sampling, respectively and 8 timepoints for the intensive PK sampling at a later visit). Therefore, the maximum PK sample volume for a given participant in the intensive PK sampling group will be approximately 72 mL. This volume will be lower for patients participating only in the sparse PK sample collection and will be approximately 24 mL (2 samples on Day 29 and 2 samples on Day 57).

CONFIDENTIAL

The information contained herein may not be used, disclosed, or published without the written consent of
Biogen MA Inc.

10. SAFETY ASSESSMENTS

See Section 1.3 for the timing of all safety assessments.

Tests and evaluations affecting primary endpoints and/or analyses may need to be repeated if the original results are lost or damaged. In these cases, participants will be asked to return to the study site to have the evaluations repeated.

10.1. Clinical Safety Assessments

The following clinical assessments will be performed to evaluate the safety profile of DRF:

- AE and SAE recording
- Medical history
- Physical examinations: Full physical examinations will be performed at Screening. An abbreviated physical examination (i.e., examination of general appearance and the following body systems: lymph nodes, thorax and lungs, cardiovascular system, abdomen, and skin) will be performed at other timepoints.
- Vital sign measurements: temperature, pulse rate, systolic and diastolic blood pressure, and respiratory rate
- Weight and height measurements
- 12-lead ECGs
- C-SSRS
- Concomitant therapy and procedure recording

10.2. Laboratory Safety Assessments

Samples will be analyzed using Good Laboratory Practice-validated assays.

The following laboratory assessments will be performed to evaluate the safety profile of DRF:

CONFIDENTIAL

The information contained herein may not be used, disclosed, or published without the written consent of
Biogen MA Inc.

Table 5: Clinical Laboratory Assessments

Hematology ¹	Biochemistry	Urinalysis
Hematocrit	Sodium	Color
Hemoglobin	Potassium	pH
Red blood cell count	Chloride	Specific gravity
Total and differential (absolute)	Bicarbonate	Ketones
white blood cell count	Glucose	Protein
Platelets	Calcium	Glucose
	Uric acid	Bilirubin
	Creatinine ²	Nitrite
	Total protein	Urobilinogen
	Blood urea nitrogen	Occult blood
	Albumin	Microscopic examination of sediment only if urinalysis dipstick results are abnormal
	Total bilirubin	Urine albumin
	ALT	Urine beta-2-microglobulin
	AST	Urine creatinine
	LDH	
	Alkaline phosphatase	
	GGT	
	Creatine phosphokinase	
	Lipid profile: blood cholesterol, high-density lipoprotein, low-density lipoprotein, and triglycerides	
	Serum FSH (to confirm postmenopausal status) ³	
	Vitamin D (1,25-(OH) ²)	
	TSH ³	
	Serum pregnancy ⁴	
	HIV/Hepatitis screen ³	
	TB test ³	

¹ Additional hematology assessments will be collected for participants requiring follow-up for lymphopenia at the time of study completion or ET.

² Serum creatinine will be used to calculate eGFR at each timepoint that a creatinine result is generated. Participant's latest weight assessment will be used to calculate eGFR.

³ Only at Screening.

⁴ Only at Screening and Safety Follow-Up (Visit 15).

CONFIDENTIAL

The information contained herein may not be used, disclosed, or published without the written consent of Biogen MA Inc.

11. SAFETY DEFINITIONS, RECORDING, REPORTING, AND RESPONSIBILITIES

Throughout the course of the study, every effort must be made to remain vigilant to possible AEs. If an AE occurs, the first concern should be for the safety of the participant. If necessary, appropriate medical intervention should be provided.

At the signing of the ICF, each participant and/or his/her legally authorized representative and/or main caregiver must be given the names and telephone numbers of site staff for reporting SAEs, pregnancies, overdoses, and medical emergencies. Throughout the protocol, the Sponsor is named, but reporting may be done through a CRO.

11.1. Definitions

11.1.1. Adverse Event

An AE is any untoward medical occurrence in a patient or clinical investigation participant (participant) administered a pharmaceutical product and that does not necessarily have a causal relationship with this treatment. An AE can therefore be any unfavorable and unintended sign (including an abnormal assessment such as an abnormal laboratory value), symptom, or disease temporally associated with the use of a medicinal (investigational) product, whether or not related to the medicinal (investigational) product.

Determination of whether an abnormal assessment (e.g., laboratory value, vital sign, and ECG) result meets the definition of an AE will be made by the Investigator. Abnormal results are not considered AEs unless one or more of the following criteria are met:

- The result meets the criteria for an SAE.
- The result requires the participant to receive specific corrective therapy.
- The result is considered by the Investigator to be clinically significant.

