5.7.2. Adverse Events

An overview table, including number of participants with any TEAEs, TEAEs by severity, study treatment-related TEAEs, SAEs, study treatment-related SAEs, TEAEs

leading to drug interruption or dose reduction, TEAEs leading to study withdrawal or study treatment discontinuation will be provided by cohort and overall. SAEs leading to death will be summarized in the same table.

The incidence of TEAEs will be summarized for each cohort and overall, as follows:

- TEAEs by system organ class and preferred term (sorted by decreasing frequency and alphabetical order)
- TEAEs by system organ class
- TEAEs by preferred term
- TEAEs experienced by $\geq 5\%$ of participants by preferred term
- TEAEs by 4-week intervals by preferred term
- TEAEs of Special Interest by System Organ Class and Preferred Term
- Severe TEAEs by system organ class and preferred term
- Severe TEAEs by preferred term
- TEAEs by maximum severity by system organ class and preferred term
- TEAEs by maximum severity by preferred term
- Related TEAEs by system organ class and preferred term
- TEAEs that led to discontinuation of study treatment by system organ class and preferred term
- TEAEs that led to withdrawal from study by system organ class and preferred term
- TEAEs that led to drug dose reductions or interruptions by system organ class and preferred term
- TESAEs by system organ class and preferred term
- TESAEs by preferred term
- Related TESAEs by system organ class and preferred term

All AEs will be included in the participant-level listings. Supporting listings of SAEs, AEs leading to study treatment discontinuation, AEs leading to withdrawal from study, and AEs leading to death will be provided.

If more than one event occurred with the same preferred term for the same participant, the participant will be counted only once for that preferred term using the most severe occurrence for the summary table by severity. Similarly, if a participant has the same AE on multiple occasions, the closest relationship to study drug recorded for the event will be presented in the summary table for related events.

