5.7.3. Adverse Events of Special Interest

Anaphylaxis and angioedema (serious events), PML (all events), Pancreatitis (all events), Serious and Opportunistic infections (serious events), Infections (serious), Lymphopenia and leucopenia (serious events), Liver injury (serious events and events leading to

treatment discontinuation), Pre-malignant conditions (all events), Malignancies (all events), Renal tubular injury (serious events), GI disorder (serious events or events leading to treatment discontinuation), Flushing and related events (serious events) and Cardiac disorders (all events).

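### A laboratory result that forces study treatment to be withheld or stopped is not by itself an AE, so a mandated temporary hold can be missing from AE incidence and from the SAP's interruption table

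*Protocol*

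**What the plan says.** Protocol Section 11.1.1 leaves it to the Investigator whether an abnormal assessment is an AE, within a closed list: "Abnormal results are not considered AEs unless one or more of the following criteria are met". The three criteria are "The result meets the criteria for an SAE", "The result requires the participant to receive specific corrective therapy" and "The result is considered by the Investigator to be clinically significant". No redaction is visible in the list.

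Protocol Section 8.1 is automatic by contrast: "study treatment must be temporarily withheld if any of the following laboratory parameters meet the following threshold limits". The limits, each confirmed by repeat testing, are AST or ALT > 3 x ULN, eGFR < 60 mL/min/1.73 m², and urine albumin/creatinine ratio > 22.6 mg/mmol. If the value stays beyond its limit for at least 4 "weeks after interruption of study treatment, the participant must permanently discontinue study treatment". A separate bullet requires a permanent stop, with no preceding hold, for lymphocytes < 0.5 x 10³/µL lasting more than 6 months. None of these rules says that the result is to be recorded as an AE. Stopping because of an AE is a different bullet.

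SAP Section 5.7.2 plans "TEAEs that led to drug dose reductions or interruptions by system organ class and preferred term" and a matching table for discontinuation. SAP Section 5.7.3 limits the liver category of special interest to "Liver injury (serious events and events leading to" treatment discontinuation, and renal tubular injury to serious events. Every one of these outputs needs an AE record.

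**The concern.** AE incidence is a primary endpoint of both parts, and in a single-arm study the events that interrupt or end treatment are a main measure of tolerability. Section 8.1 acts on a number; Section 11.1.1 asks for a judgement. Two participants with the same confirmed value and the same mandated hold can therefore be counted differently because two sites answered the significance question differently.

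Compared with a rule that counts every mandated hold, the difference has one direction: the reported incidence can only be lower. There is no concurrent control arm to share it. Protocol Section 12.5 also allows descriptive comparison of selected safety data with Studies ALK8700-A301 and 109MS305, so the recording rule affects how those comparisons read.

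**Working it through.** No stated figure is in dispute, so the check traces each Section 8.1 trigger through the definitions and the planned outputs.

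**1. Does any 11.1.1 criterion necessarily catch a trigger?** The first does so only if the result is serious. The second needs a therapy to be given, and withholding the study drug is not a therapy received. That leaves Investigator judgement as the only route for a non-serious, untreated laboratory breach.

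**2. Does the protocol accept 'not clinically significant' at these limits?** For one trigger, yes. Exclusion criterion 30b uses the same albumin/creatinine limit, > 22.6 mg/mmol. The note after it, repeated in Section 6.3.2, provides for out-of-range values that the Investigator finds not clinically significant. For eGFR, exclusion 29c is ≤ 60. A participant may enter at 61, fall to a confirmed 59 and be held, and the same judgement is plausible.

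**3. Where does each trigger show if no AE is recorded?**

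| Section 8.1 trigger | Consequence | Row in SAP Table 3 (PCS) |
|---|---|---|
| ALT > 3 x ULN | hold, then stop if persistent | yes, > 3 x ULN |
| AST > 3 x ULN | hold, then stop if persistent | yes, ≥ 3 x ULN |
| eGFR < 60 | hold, then stop if persistent | none (creatinine ≥ 176.8 µmol/L only) |
| Albumin/creatinine ratio > 22.6 mg/mmol | hold, then stop if persistent | none (urine protein ≥ ++ only) |
| Lymphocytes < 0.5 for > 6 months | stop | yes, < 0.5 (value, not duration) |

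Shift tables and listings of abnormal values (SAP 5.7.4) add to this, but like the PCS rows they show values, not actions taken. Permanent stops are tabulated by reason (SAP 5.2). Temporary holds have no such table, and exposure (SAP 5.5) runs from first to last dose, ignoring interruptions.

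**4. What does percent compliance show?** In SAP 5.5, expected capsules are 2 a day in the first week and 4 a day afterwards, over days in the study. Taking Part 1 as 24 x 7 = 168 days: expected = 7 x 2 + 161 x 4 = 658. A 28-day hold at full dose removes 28 x 4 = 112. Compliance = (658 - 112) / 658 = 546 / 658 = 83.0%. The hold is visible, but it looks the same as 112 missed capsules, or as 56 days on a reduced dose of 2 capsules a day.

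**5. Can the lymphocyte rule act in Part 1?** Six months is about 6 x 365 / 12 = 182.5 days. Even if counted from Day 1, more than 6 months ends after Day 183. The Week 24 window closes on Day 169 + 5 = Day 174. The rule can matter only after Week 24.

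**6. Is SAE incidence affected?** No. Any result meeting SAE criteria is an AE under the first criterion. The plan's 87% reproduces, 1 - 0.96^50 = 0.870, and does not depend on this point.

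**7. Size.** Expected uncounted participants = N x h x s, where h is the share meeting a limit and s the share of those judged not clinically significant. The documents give neither. As assumptions only, h from 2% to 10% and s from 25% to 75% give 50 x 0.02 x 0.25 = 0.25 to 50 x 0.10 x 0.75 = 3.75 participants per cohort of 50. The effect on the any-TEAE row would be at most this, because anyone with another TEAE is already counted.

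**The case against.** The strongest reply is that the third criterion already covers these cases. Exclusion criteria 14 and 28 explain clinical significance in terms of confounding results or posing risk to the participant, and a repeat-confirmed value that triggers a safety hold fits that description. Many Investigators would record it. This stands as a reason to expect that the loss is not universal. It does not close the gap: that explanation belongs to eligibility, 11.1.1 does not repeat it, and the protocol itself allows for a non-significant value above the albumin/creatinine hold limit.

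The second reply is that laboratory change is also a primary endpoint, with its own outputs. This stands in large part. A reader might infer that Section 8.1 holds and stops disappear from the report. The documents do not support that: ALT, AST and lymphocyte values have PCS rows, shift tables and listings; permanent stops appear by reason; dosing information goes on the dosing CRF. Creatinine and urine protein give partial cover for the two renal triggers.

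A reader might also infer that follow-up lapses, because the duty in 11.3.1 to follow until resolution attaches to AEs. Section 8.1 has its own repeat testing and 4-week persistence check, laboratory tests are scheduled throughout treatment, and low lymphocytes have monitoring visits. That inference should not be drawn.

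Finally, parts of Sections 7.2 and 11.3.1 are blacked out and the eCRF is not available. If text there makes a mandated hold an AE, a cross-reference from 11.1.1 would be enough.

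**Conclusion.** The point holds in a limited form. Following the plan exactly, a participant can have treatment withheld under a protocol safety rule with no AE record, and that hold is then missing from AE incidence and from the only table that reports interruptions. The real exposure is temporary holds, chiefly for eGFR and albumin/creatinine ratio. For permanent stops the loss is confined to the AE-based tables, including the non-serious liver category of special interest.

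The undercount is possible rather than certain, depends on site judgement, and runs only downward. Its size cannot be derived from the documents; the range in the working is arithmetic on assumed rates and is no estimate. A reader might be tempted to set it against the 4% SAE rate used for the sample size. That comparison is not supported, because serious results are captured in any case. This is a cheap improvement to recording or reporting, not a flaw that undermines the primary analysis.

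**What to change.** Either of two changes is enough; neither alters a Section 8.1 threshold or rule.

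- **In the protocol:** add a fourth criterion to 11.1.1: *The result leads to study treatment being withheld or permanently discontinued (Section 8.1).* With the action taken recorded on the AE form, the existing SAP tables capture these cases unchanged. The cost is one sentence in the protocol and one in the CRF completion guide, a few more laboratory AEs, and a slightly less favourable reported incidence. If participants have already been treated, the criterion must also be applied to earlier holds, or the counts will mix two rules.
- **In the SAP, if the AE definition is to stay as it is:** add to Section 5.7 a table and listing, by cohort and overall, of all Section 8.1 laboratory-triggered holds and stops regardless of AE status, giving the trigger, the action and whether an AE was recorded. The cost is one more table and listing, built from laboratory data and the dosing records, provided the eCRF identifies holds.
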